8.4.2. Vital Signs

Vital sign parameter (systolic blood pressure, diastolic blood pressure, pulse rate and heart rate) change from baseline at every assessed time point will be summarized (n, mean, standard deviation, median, minimum, and maximum). The number of subjects with worst case vital sign results relative to normal range criteria which are post-baseline relative to baseline will be summarized by test and category. A by-subject listing of vital signs for all participants with potential clinical importance will be produced. Potential clinical importance criteria are specified in [Appendix 8: Values of Potential Clinical Importance](#).

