9.4.2. Vital Signs

- Pulse rate, respiratory rate, and blood pressure will be assessed.

- Blood pressure and pulse measurements will be assessed with a completely automated device. Manual techniques will be used only if an automated device is not available.
- Blood pressure and pulse measurements should be preceded by at least 5 minutes of rest for the participant in a quiet setting without distractions (eg, television, cell phones).
- Vital signs will be measured in a semi-supine position after 5 minutes rest and will include, systolic and diastolic blood pressure, and pulse and respiratory rate. Three readings of blood pressure and pulse will be taken. The first reading should be rejected. The second and third readings should be averaged to give the measurement to be recorded in the CRF.

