9.4.3. Electrocardiograms

- Triplicate and Single 12-lead ECG will be obtained as outlined in the SOA (see Section 2) using an ECG machine that automatically calculates the heart rate and measures PR, QRS, QT, and QTcF intervals. Refer to Section 8.1.2 for QTcF withdrawal criteria and additional QTcF readings that may be necessary.
- At each time point at which triplicate ECG are required, 3 individual ECG tracings should be obtained as closely as possible in succession, but no more than 2 minutes apart. The full set of triplicates should be completed in less than 4 minutes.

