2. SUMMARY OF KEY PROTOCOL INFORMATION

2.1. Changes to the Protocol Defined Statistical Analysis Plan

There were no changes or deviations to the originally planned statistical analysis specified in the protocol (Dated: 26/AUG/2019 Version: 208132/03).

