2.2. Study Objective(s) and Endpoint(s)

Objectives	Endpoints
Primary Objectives	Primary Endpoints

 To evaluate the antiviral activity of GSK3640254 in HIV-1 infected Treatment-Naïve(TN) participants during 10 days of monotherapy in Part 1 and during 7 days of monotherapy in Part 2 	
 Maximum change from baseline (Day 1) in plasma HIV-1 ribonucleic acid (RNA)
Secondary Objectives	Secondary Endpoints

 To assess the safety and tolerability of GSK3640254 when administered as monotherapy over 10 days in Part 1 and over 7 days in Part 2 in HIV-1 infected TN participants 	
 GSK3640254 safety and tolerability parameters: adverse events (AE) ; post-baseline values and changes over time of clinical laboratory evaluations, vital signs, and electrocardiogram (ECG) parameters

 To characterize the pharmacokinetics of GSK3640254 dosing for 10 days in Part 1 and for 7 days in Part 2 in HIV-1 infected patients 	
 GSK3640254 PK parameters at the following dose administration: Day 1: area under the plasma concentration time curve from zero to 24 (AUC[0-24]), maximum observed concentration (C_{max}), time to maximum observed concentration (t_{max}), concentration at 24 hours post dose (C₂₄), absorption lag time (t_{lag}). Following repeat administration: Area under the curve (Area under the plasma drug concentration-time curve from pre-dose to the end of the dosing interval at steady state (AUC[0-τ]), C_{max}, t_{max}, pre-dose concentration (C₀), concentration at end of dosing interval (C_τ), apparent terminal phase half-life (t_{1/2}), and apparent oral clearance (CL/F), if data permit.

 To explore the relationship between GSK3640254 exposure and change in plasma HIV-1 RNA 	
 GSK3640254 repeat-dose PK parameters AUC(0-τ), C_{max}, C_τ with maximum HIV-1 RNA change from baseline

 To estimate GSK3640254 accumulation following administration of GSK3640254 for 10 days in Part 1 and for 7 days in Part 2 in HIV-1 infected patients 	
 Accumulation: GSK3640254 PK accumulation ratios (R): repeat -dose AUC (0-τ), C_{max}, and C_τ compared to Day 1 AUC (0-24), C_{max}, C₂₄, respectively

CONFIDENTIAL

208132

Objectives	Endpoints

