13.8. Appendix 8: Values of Potential Clinical Importance

Haematology					
Laboratory Parameter	Units	Category	Clinical Concern Range		
			Low Flag (< x)	High Flag (>x)	
Hematocrit	Ratio of 1	Male		0.54	
		Female		0.54	
		Δ from BL	↓0.075		
Hemoglobin	g/L	Male		180	
		Female		180	
		Δ from BL	↓25		
Lymphocytes	x10 ⁹ /L		0.8		
Neutrophil Count	x10 ⁹ /L		1.5		
Platelet Count	x10 ⁹ /L		100	550	
White Blood Cell Count (WBC)	x10 ⁹ /L		3	12	
Clinical Chemistry					
Laboratory Parameter	Units	Category	Clinical Concern Range		Comments
			Low Flag (< x)	High Flag (>x)	
Bicarbonates	mmol/L		18	32	
BUN	mmol/L			9	
Calcium	mmol/L		2	2.75	
Chloride	mmol/L		98	107	
Creatinine	μmol/L	Δ from BL		44.2	
Glucose	mmol/L		3	11	
Potassium	mmol/L		3	5.5	
Sodium	mmol/L		130	150	
Total Protein	g/L	Δ from BL	-15	15	
Liver Function					
Test Analyte	Units	Category	Clinical Concern Range		
ALT/SGPT	U/L	High	≥ 2x ULN		
AST/SGOT	U/L	High	≥ 2x ULN		
AlkPhos	U/L	High	≥ 2x ULN		
Total Bilirubin	μmol/L	High	≥ 1.5xULN		

CONFIDENTIAL

208132

ECG

ECG Parameter	Units	Clinical Concern Range	
		Lower	Upper
Absolute			
PR Interval	msec	< 120	> 200
QRS Duration	msec	< 60	> 120
QT Interval	msec	< 320	> 450
QTc Interval (Bazett)	msec	< 320	> 450
QTc Interval (Fridericia)	msec	< 320	> 450
RR Interval	msec	< 600	> 1200
Change from Baseline			
Increase from Baseline QTc	msec		>60

Vital Signs

Vital Sign Parameter (Absolute)	Units	Clinical Concern Range	
		Lower	Upper
Systolic Blood Pressure	mmHg	< 85	> 140
Diastolic Blood Pressure	mmHg	< 45	> 90
Heart Rate	bpm	< 40	> 100

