3.40.	Safety	LIVER10	Summary of Hepatobiliary Laboratory Abnormalities – Part 2	IDSL	SAC
3.41.	Safety	SAFE_T2	Summary of Treatment Emergent Liver Toxicities – Part 1		SAC
3.42.	Safety	SAFE_T2	Summary of Treatment Emergent Liver Toxicities – Part 2		SAC
ECG					
3.43.	Safety	EG1	Summary of ECG Findings – Part 1	IDSL	HL. SAC
3.44.	Safety	EG1	Summary of ECG Findings – Part 2	IDSL	HL. SAC
3.45.	Safety	EG2	Summary of Change from Baseline in ECG Values by Visit – Part 1	IDSL	SAC
3.46.	Safety	EG2	Summary of Change from Baseline in ECG Values by Visit – Part 2	IDSL	SAC
3.47.	Safety	EG10	Summary of Maximum QTc Values Post-Baseline Relative to Baseline by Category – Part 1	IDSL	SAC
3.48.	Safety	EG10	Summary of Maximum QTc Values Post-Baseline Relative to Baseline by Category – Part 2	IDSL	SAC

CONFIDENTIAL

208132

Safety: Tables					
No.	Population	IDSL / Example Shell	Title	Programming Notes	Deliverable [Priority]
3.49.	Safety	EG11	Summary of Maximum Increase in QTc Values Post-Baseline Relative to Baseline by Category – Part 1	IDSL	SAC
3.50.	Safety	EG11	Summary of Maximum Increase in QTc Values Post-Baseline Relative to Baseline by Category – Part 2	IDSL	SAC
3.51.	Safety	ING111207, Table 10.30	Listing of QTc Interval Data for Subjects with QTc Measurement > 500msec or Increase from Baseline > 60msec- Part 1 and 2	For subjects with QTcB or QTcF measurement > 500msec or increase from baseline > 60msec, list QTcB and QTcF data (both value and change from baseline) at all time points, and flag the values > 500msec and increases > 60msec	SAC
Vital Signs					
3.52.	Safety	VS1	Summary of Change from Baseline in Vital Signs – Part 1	ICH E3	SAC
3.53.	Safety	VS1	Summary of Change from Baseline in Vital Signs – Part 2	ICH E3	SAC
3.54.	Safety	VS3	Summary of Worst-Case Vital Signs Relative to Normal Range Post-Baseline Relative to Baseline – Part 1	IDSL	SAC
3.55.	Safety	VS3	Summary of Worst-Case Vital Signs Relative to Normal Range Post-Baseline Relative to Baseline – Part 2	IDSL	SAC
C-SSRS					
3.56.	Safety	CSSRS4	Listing of C-SSRS Suicidal Ideation or Behaviour Data	IDSL. Part 1 and Part 2 in one table.	SAC

CONFIDENTIAL

208132

Safety: Tables					
No.	Population	IDSL / Example Shell	Title	Programming Notes	Deliverable [Priority]
cART					
3.57.	Safety	CM1	Summary of cART Medications ATC Categories by Ingredient – Part 2	IDSL. Part 2 only.	SAC

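### The SAP's list of vital signs for the change-from-baseline summary leaves out respiratory rate, which the protocol measures, and appears to name one rate twice

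*SAP*

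**What the plan says.** Protocol section 9.4.2 states twice what is measured as a vital sign. It opens with "Pulse rate, respiratory rate, and blood pressure will be assessed". The procedure bullet then says that the measurements "will include, systolic and diastolic blood pressure, and pulse and respiratory rate". Neither statement is limited to particular visits. Both schedules of activities carry a single vital-signs row that is not split by parameter.

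SAP section 8.4.2 plans descriptive statistics for "Vital sign parameter (systolic blood pressure, diastolic blood pressure, pulse rate and heart rate) change from baseline at every assessed time point". It then plans a worst-case summary against the normal range by test and category, and a listing for participants with values of potential clinical importance. Neither of those two sentences names parameters.

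The endpoint served is in SAP section 2.2 (and protocol section 4), where the secondary safety endpoint includes "post-baseline values and changes over time of clinical laboratory evaluations, vital signs, and electrocardiogram (ECG) parameters". No vital sign is excluded from it.

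**The concern.** The parenthesis in SAP 8.4.2 reads as a complete list. It has four entries, as the protocol has four measures, but the entries differ. Two of the SAP's entries, pulse rate and heart rate, look like the same quantity, and the second stands where respiratory rate would be expected. That has the look of a drafting slip.

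A programmer who follows the list would produce the change-from-baseline tables without respiratory rate. Part of a secondary safety endpoint would then be collected from every participant and left out of the table designed to report it, without any stated decision to do so.

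**Working it through.** The plan gives no figure to reproduce here. The check compares what is collected with what is planned for analysis, then looks for any display that would make good the gap.

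**Step 1: compare the lists.**

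| Measure | Protocol 9.4.2 (collected) | SAP 8.4.2 (change from baseline) |
|---|---|---|
| Systolic pressure | yes | yes |
| Diastolic pressure | yes | yes |
| Pulse rate | yes | yes |
| Respiratory rate | yes | no |
| Heart rate | not listed under this name | yes |

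Three of the four collected measures are on the SAP list. Respiratory rate is the one missing.

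**Step 2: look for respiratory rate elsewhere in the SAP.**

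- *Tables 3.52 and 3.53.* These are the change-from-baseline tables, one per part, titled "Summary of Change from Baseline in Vital Signs". The titles name no parameter, so the list in 8.4.2 is what defines their content.
- *Tables 3.54 and 3.55.* These are the worst-case tables. They also name no parameter, and the sentence behind them in 8.4.2 is not restricted to the list.
- *Appendix 8.* The vital-sign limits cover systolic pressure, diastolic pressure and heart rate. There is no entry for respiratory rate.
- *Listing 30.* This is the only vital-sign listing. It shows all vital-sign data, but only for participants with a value of potential clinical importance. With no entry in Appendix 8, a respiratory-rate value cannot bring a participant into it.
- *Listings 32 to 56.* None is a vital-sign listing.

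The SAP text does not mention respiratory rate anywhere. Two routes remain by which it might be shown: the general worst-case tables, and Listing 30 for a participant flagged on blood pressure or heart rate.

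**Step 3: count the readings.** The inputs are the schedules of activities and the planned sample size (protocol section 5.2).

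- Part 1: vital signs at Visits 2, 3, 5 and 9 after baseline, which is 4 visits. 14 participants × 4 = 56.
- Part 2: vital signs at Visits 2, 3, 5 and 7 after baseline, which is 4 visits. 20 participants × 4 = 80.
- Total: 56 + 80 = 136, which equals 34 × 4.

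This assumes full attendance and one respiratory-rate value per visit. It counts scheduled readings and does not measure lost information.

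**The case against.** The strongest reply is that the gap may close in practice. SAP section 8.4 bases vital-sign analyses on the sponsor's core data standards, and the tables cite standard shells that are not among the documents. A programmer working from those shells might include respiratory rate. This stands for Tables 3.54 and 3.55 and partly for Listing 30, so a reader who concludes that respiratory rate is never summarised goes further than the text allows. It does not rescue Tables 3.52 and 3.53: the deferral to standards applies only where nothing else is specified, and 8.4.2 does specify a list.

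A reader might also infer that heart rate is not collected, or that the pulse is not screened because Appendix 8 sets limits for heart rate only. The documents support neither inference. Protocol 9.4.3 records ECGs "using an ECG machine that automatically calculates the heart rate", so heart rate is collected. Footnote 1 to the ECG exclusion table in protocol 6.2 lets a heart rate be rechecked by ECG or by vital signs, so the protocol itself uses the term for the pulse. The Appendix 8 row is in beats per minute under vital signs, while the ECG block uses RR interval. The row reasonably covers the pulse.

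Finally, SAP 2.1 states "There were no changes or deviations to the originally planned statistical analysis specified in the protocol". A reader might call that false. It is not shown to be: the protocol's safety analysis section (10.3.2.1) names no vital-sign parameter, and 9.4.2 describes a measurement procedure, not an analysis.

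**Conclusion.** The point holds for the change-from-baseline summary. SAP 8.4.2 omits a vital sign that the protocol measures at every vital-sign visit, and no other SAP text restores it by name. Up to about 136 scheduled readings have no specified change-from-baseline summary.

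The weight is low. Safety is descriptive, with no formal analysis planned. Respiratory function is not among the risks named in protocol section 3.3.1. An abnormal vital sign that the investigator judges clinically significant is recorded as an adverse event under protocol Appendix 4 and reached through those tables. No dose decision or primary result depends on it.

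The conclusion rests on reading the list in 8.4.2 as complete, which is its natural sense, and on pulse and heart rate being one measure, which the protocol's own usage supports. If they were meant as two measures, respiratory rate would still be missing.

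**What to change.** In SAP 8.4.2, change the list to systolic blood pressure, diastolic blood pressure, pulse rate and respiratory rate, and make clear that Tables 3.52 to 3.55 all use it. State in 8.4.2 or Appendix 8 whether any criterion of potential clinical importance applies to respiratory rate. If none does, say so, so that its absence from Listing 30's triggers is a recorded decision. Whether one is needed is for the clinical team.

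Using one term, pulse rate or heart rate, in both 8.4.2 and Appendix 8 would be tidier but is optional; the existing limits need not change.

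The cost is a few words in the SAP and one more parameter in tables that are already planned. No new data are needed.

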8.4.3. Columbia Suicide Severity Rating Scale (C-SSRS)

Summaries of Columbia Suicide Severity Rating Scale (CSSRS) will be produce for each treatment group in Part 1 and Part 2.

8.4.4. Combination anti-retroviral therapy (cART)

In Part 2 of the study, participant must be willing and able to start cART on Study Day 8. Summary and listing of cART medication will be produced accordingly.

9. PHARMACOKINETIC ANALYSES

Unless specified, pharmacokinetic analyses tables will be reported separately for Part 1 and Part 2. Listings will be paginated by part, sorted by participant, day, time, and noting treatment.

9.1. Primary Pharmacokinetic Analyses

9.1.1. Endpoint / Variables

9.1.1.1. Drug Concentration Measures

Refer to [Appendix 5: Data Display Standards & Handling Conventions \(Section 13.5.3 Reporting Standards for Pharmacokinetic\)](#)

9.1.1.2. Derived Pharmacokinetic Parameters

Pharmacokinetic parameters will be calculated by standard non-compartmental analysis according to current working practices and using the currently supported version of WinNonlin Version 6.1 or higher. All calculations of non-compartmental parameters will be based on actual sampling times. Pharmacokinetic parameters listed will be determined from the plasma concentration-time data, as data permits.

Parameter	Parameter Description
Visit 1 (Day 1)	
AUC(0-24)	Area under the concentration-time curve from time zero to the concentration at 24-hour post dose. AUC will be calculated using the linear trapezoidal rule for each incremental trapezoid and the log trapezoidal rule for each decremental trapezoid.
C _{max}	Maximum observed concentration, determined directly from the concentration-time data.
C ₂₄	Concentration at 24 hours post dose
t _{max}	Time to reach C _{max} , determined directly from the concentration-time data.
t _{lag}	absorption lag time
Visit 5 (Day 8, 9 or 10 for Part 1 and Day 7 for Part 2)	
AUC(0-τ)	Area under the concentration-time curve over the dosing interval. AUC will be calculated using the linear trapezoidal rule for each incremental trapezoid and the log trapezoidal rule for each decremental trapezoid.
C ₀	Concentration at pre-dose
C _τ	Concentration at the end of the dosing interval
C _{max}	Maximum observed concentration, determined directly from the concentration-time data.
t _{max}	Time to reach C _{max} , determined directly from the concentration-time data.
λ _z	The slope of the apparent terminal phase
t _{1/2}	Apparent terminal half-life will be calculated as: $t_{1/2} = \ln 2 / \lambda_z$
CL/F	Apparent oral clearance will be calculated as: $CL/F = \text{Dose} / AUC(0-\tau)$

CONFIDENTIAL

208132

Parameter	Parameter Description
R_AUC	The accumulation ratio of AUC will be calculated as: will be calculated as: $R_AUC = AUC(0-\tau) \text{ Visit 5} / AUC(0-24) \text{ Visit 1}$
R_Cmax	The accumulation ratio of Cmax will be calculated as: will be calculated as: $R_Cmax = Cmax \text{ Visit 5} / Cmax \text{ Visit 1}$
R_C τ	The accumulation ratio of C τ will be calculated as: will be calculated as: $R_C\tau = C\tau \text{ Visit 5} / C24 \text{ Visit 1}$

NOTES:

- Additional parameters may be included as required.

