A qualified participant will be randomized into the treatment phase of the study and will administer study treatments, once daily, from Day 1 through Day 10 in Part 1 and from Day 1 through Day 7 in Part 2. On Day 1, an appropriate number of bottles will be dispensed, with a supply sufficient to cover the entire treatment period. The blinded bottles will contain capsules of either the active dose or placebo. Dosing instructions will be indicated on each bottle. Participants will bring the bottles of study treatments to each visit, so that study treatment can be administered in the clinic after the study procedures have been performed.

Each dose of study medication will be taken with approximately 240 mL (8 ounces) of water following ingestion of a moderate calorie and fat meal (i.e. at least 400 calories, with at least 120 calories from fat), that is required to be completed within 30 minutes prior to dosing. A moderate calorie and fat breakfast is planned to be similar to the following (additional meal suggestions will be included in the Study Reference Manual [SRM]):

- 2 slices of bread
- 10 g of butter
- 20 g of jam
- 15 g of cheese
- 175 mL of apple juice

Study treatments should be administered near the same time each morning, within a 2-hr window.

On days when the participant self-administers the study treatments, observed dosing with a site staff member may be achieved as locally permitted using various forms of video calling (when at all possible) such as FaceTime, Skype, WhatsApp.

Participants will then enter the post-dosing period:

Study Part 1:

There are 4 in-clinic visits in the Part 1 post-dosing period: 3 visits for PK and other assessments during the 7 days immediately following the last dose, and a final follow-up visit primarily for safety (e.g., to follow any AEs to resolution) approximately 8-14 days after the last dose, as shown in the Part 1 Schedule of Activities (SOA, Section 2). In Part 1, participants should not start other medicines and will not start ARVs during the post-dosing period until they have completed the final follow-up visit.

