Preliminary GSK3640254 PK parameters derived based on nominal sampling times following single doses of 1 mg to 700 mg administered after a moderate calorie and fat breakfast show GSK3640254 is slowly absorbed with a median T_{max} observed between 3-4.5 hours after dosing with a moderate fat breakfast and slowly eliminated with a mean half-life ranging from 22-26 hours. In general, exposure (maximum observed concentration [C_{max}] and area under the curve [AUC]) increased in a close-to-dose-proportional manner from 1 mg to 400 mg with no further increase in exposure at 700 mg.

Repeat dose preliminary PK parameter following once-daily administration of 50 to 320 mg QD for 14 days were determined on Day 1 and Day 14 and show a median T_{max} ranging between 3.8 to 4.3 hours. The mean half-life ranged from approximately 22 to 29 hours. Overall, there was a trend of a slightly less than dose-proportional increase in C_{max} and AUC(0-24) from 50 to 320 mg. The exposure on Day 14 was, on average, 1.9 to 2.3 fold higher than that of Day 1 for C_{max} and 2.2 to 2.6 fold higher than Day 1 for

AUC(0-24). Detailed summary statistics are available in the Study Synopsis [GSK Document Number [2018N375461_00](#)].

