9.5. Pharmacokinetics

- Whole blood samples of approximately 5 mL will be collected for measurement of plasma concentrations of GSK3640254 as specified in the SOA. A maximum of 5 samples may be collected at additional time points during the study if warranted and agreed upon between the investigator and the sponsor. Instructions for the collection and handling of biological samples will be provided by the sponsor. The actual date and time (24-hour clock time) of each sample (as well as each subsequent dose) will be recorded.
- Samples will be used to evaluate the PK of GSK3640254. Each plasma sample will be divided into aliquots as outlined in the laboratory manual. Samples collected for analyses of GSK3640254 plasma concentration may also be used to evaluate safety or efficacy aspects related to concerns arising during or after the study.
- Once the plasma has been analysed for GSK3640254, any remaining plasma may be analysed for other compound-related metabolites and the results reported under a separate protocol.

Drug concentration information that may unblind the study will not be reported to investigative sites or blinded personnel until the study has been unblinded.

Intensive PK sampling (Clinic Visit 1 and Clinic Visit 5) begins with a morning pre-dose sampling, i.e, prior to the administration of the morning dose of the study treatment on the day of the visit. The pre-dose sampling should be done approximately 24 hours after the morning doses of the study drugs were taken the day prior to the visit. This pre-dose blood sampling will include the collection of the other parameters as well.

The subsequent 8 time points include samplings through Hour 12, with a final sample collected at Hour 24. The subject will either stay overnight or will return to the clinic so that the final sample can be collected at Hour 24.

It is critical to capture the exact date and time of each PK sample collection, even if drawn slightly off-schedule. If a sample collection time point is missed/late/not done within the specified window and the next collection time point has not yet been reached, collect the missed time point, and record the exact time of that collection, then get back on track for the next time point/on-time collection.

[Table 4](#) below lists the sampling schedule to be followed for the assessment of intensive pharmacokinetics. Further details of PK blood collection and sample processing will be provided in the central clinical laboratory manual.

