	Clinic Visit 1	Clinic Visit 2	Clinic Visit 3	Virtual	Clinic Visit 4	Virtual	Virtual	Clinic Visit 5	Virtual	Virtual	Clinic Visit 6	Clinic Visit 7	Clinic Visit 8	Clinic Visit 9
Single, Pharmacokinetic (PK) sample (pre- dose at Visits 3 and 4)			X		X						X ⁷	X	X	
Intensive PK sampling ⁸ (with sample at 24hr time point the next morning)	X							X ⁹						
Observed dosing with GSK3640254/plac ebo ³	X	X	X	X	X	X	X	X	X	X				
IWRS (RAMOS) activity ¹⁰	X													

CONFIDENTIAL

208132

1. Procedures should be performed in the following order: ECG, Vitals, Blood Draws, followed by dose administration.
 2. The study requires 9 in-clinic visits. Flexibility is offered for Visits 3, 4, 5, 8 and 9. The visit schedule for each participant should be pre-planned to be sure weekend, work schedules and clinic hours are appropriately considered. No visit interval during the treatment period can be greater than 3 days.
 3. These assessments must be conducted with a participant during each day indicated, to include the days when the participant is not in the clinic. This can be done in via phone, preferably via a visual method (as locally permitted) of Skype, Facetime, WhatsApp, et. al.
 4. Physical Exam will include, at a minimum, assessments of the Skin, Heart, Lungs, and Abdomen (liver and spleen).
 5. Genotypic/Phenotypic testing will be conducted on Day 1 and Day 11 samples, with other visits tested as appropriate.
 6. Plasma samples for storage will be collected at each visit starting at Day 1, including unscheduled visits. These samples will be used when needed, such as when samples are lost or where quantity is insufficient for testing. In the event samples are not used by study completion, they will be utilized for additional research on ARV resistance and/or HIV-1 disease biology/host immune response (excluding any human genetic testing)
 7. If the Intensive PK day occurs on Day 10, do not collect the Day 11 pre-dose PK sample (as it is redundant with the 24-hr PK collection (completing the sample set started on Day 10).
 8. Intensive Plasma PK samples will be collected as outlined in Protocol Table 4 in Section 9.5
 9. If Day 8 or 9 is the Clinic Visit 5 to include the Intensive PK collection, the participant must return the following day for the 24-hr PK collection, meal and dosing. The assessments to be done as indicated on what is a “virtual visit day” should be captured as a virtual visit, even if the questions are asked in the clinic.

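### Half-life is assigned to the 24-hour Visit 5 profile, about one expected half-life long, while Part 1 samples from Day 12 and Days 13-17 feed no named parameter

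*SAP*

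**What the plan says.** Apparent terminal half-life is one of the repeat-dose secondary PK endpoints in both documents, qualified by data availability.

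- **Where it is derived.** SAP 9.1.1.2 groups parameters by visit. The slope and half-life ("Apparent terminal half-life will be calculated as" ln 2 divided by the slope) appear only under the sub-heading "Visit 5 (Day 8, 9 or 10 for Part 1 and Day 7 for Part 2". Protocol 10.3.2.3 likewise ties half-life to Day 9±1 in Part 1 and Day 7 in Part 2.
- **How long that profile is.** Protocol 9.5: "The subsequent 8 time points include samplings through Hour 12, with a final sample collected at Hour 24". If Part 1 Visit 5 falls on Day 8 or 9, "the participant must return the following day for the 24-hr PK collection, meal and dosing", so a new dose follows at 24 h. In Part 2 no PK sample is scheduled after the 24 h draw on Day 8.
- **What half-life is expected.** Protocol 3.2.2, repeat dosing in healthy participants: "The mean half-life ranged from approximately 22 to 29 hours", with median Tmax "ranging between 3.8 to 4.3 hours".
- **What else is collected.** The protocol synopsis describes the early Part 1 post-dosing visits as "3 visits for PK and other assessments during the 7 days immediately following the last dose". The schedule has single PK samples on Day 11 (not drawn separately if Visit 5 is Day 10), Day 12 and one of Days 13 to 17.
- **Qualifier.** "Pharmacokinetic parameters listed will be determined from the plasma concentration-time data, as data permits". The SAP gives no window for the slope, and no minimum number of points, minimum span or goodness-of-fit rule.

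**The concern.** A terminal slope needs a decline long enough to be distinguished from assay and sampling noise, and late enough to be past distribution. The Visit 5 profile offers about one expected half-life at best. Protocol 5.5.1 describes two-compartment kinetics, so early points may also mix distribution with elimination.

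Part 1 collects samples over several half-lives after the last dose, at visits described as being for PK, yet the plan names no parameter for the Day 12 and Day 13-17 draws. What is at stake is the quality of a stated secondary PK parameter in cohorts of six. One wild individual value can dominate the arithmetic mean, SD and CV that SAP 9.1.2 asks for.

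**Working it through.** **Inputs.** Half-life 22-29 h and median Tmax 3.8-4.3 h (protocol 3.2.2); sampling times 1, 2, 3, 4, 5, 6, 8, 12 and 24 h (protocol Table 4); Part 1 last dose on Day 10, so Day 11, Day 12 and Days 13-17 fall about 24, 48 and 72-168 h later. Residual CV is not in the documents. I assume 5%, 10% and 15%, with mono-exponential decline.

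**1. Consistency of the stated half-life.** Expected accumulation is R = 1/(1 − 2^(−24/t½)).
- 22 h gives 1.88 and 29 h gives 2.29, matching the stated 1.9-2.3 for Cmax.
- The stated 2.2-2.6 for AUC corresponds to 27-34 h, by t½ = 24·ln 2 / ln(R/(R − 1)).

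So 22-29 h is a reasonable working range, if anything slightly short.

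**2. Span in half-lives** (window divided by 29 h and by 22 h).
- 0-24 h: 24/29 = 0.83 to 24/22 = 1.09
- 4-24 h: 20/29 = 0.69 to 20/22 = 0.91
- 8-24 h: 16/29 = 0.55 to 16/22 = 0.73
- Part 1, 24-72 h after the last dose: 48/29 = 1.7 to 48/22 = 2.2
- Part 1, 24-168 h: 144/29 = 5.0 to 144/22 = 6.5

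**3. Precision of one participant's estimate.** For log-linear regression SE(λ) = σ/√Sxx, with σ = √ln(1 + CV²) and Sxx the sum of squared deviations of the sampling times. The 95% range of t½ is ln 2/(λ ± 1.96·SE). For t½ = 25.5 h, λ = 0.02718; at 10% CV, σ = 0.0998.
- 8, 12, 24 h: Sxx = 138.67, SE = 0.0998/11.78 = 0.00847, λ from 0.0106 to 0.0438, t½ from 15.8 to 65.5 h.
- 24, 48, 72 h: Sxx = 1152, SE = 0.0998/33.94 = 0.00294, λ from 0.0214 to 0.0329, t½ from 21.0 to 32.4 h.

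| Samples | CV 5% | CV 10% | CV 15% |
|---|---|---|---|
| 8, 12, 24 h | 19.5-36.7 h | 15.8-65.5 h | 13 to about 290 h |
| 5, 6, 8, 12, 24 h | 20.7-33.2 h | 17.4-47.6 h | 15.1-83 h |
| 24, 48, 72 h after last dose | 23.1-28.5 h | 21.0-32.4 h | 19.4-37.3 h |
| 24, 48, 120 h after last dose | 24.3-26.9 h | 23.1-28.4 h | 22.1-30.1 h |

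The 290 h figure is unstable (simulation gives about 280-290 h) because the lower limit of the slope is close to zero. At 10% CV, a true half-life of 22 h gives 14-47 h from 8-24 h against 19-27 h from 24-72 h; for 29 h the ranges are 17-95 h and 23-38 h.

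**4. Possible bias, indicative only.** In protocol Table 2, predicted Cmax/C24 is about 2.0 at every dose (for example 1629/809 = 2.01). With Tmax near 4 h, the within-interval half-life is about 20·ln 2/ln 2.01 = 19.9 h, and 19-20 h across doses and the Tmax range. That is below 22-29 h, as a short window under two-compartment disposition could produce. These are predicted means, not individual slopes.

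**5. Where each Part 1 post-dose sample goes.**
- Day 11 is used: it is in the steady-state model (SAP 9.1.4.2.1), and it is the 24 h point when Visit 5 is Day 10 (protocol Table 4, footnote 2).
- Day 12 and Days 13-17 reach the concentration displays and listings only.

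**The case against.** The strongest reply has five parts.

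- **The 0-24 h limit is not written.** A reader might infer that the SAP confines the slope to that interval. It does not say so. The limit is inferred from the visit heading, alongside wording that allows for data availability and additional parameters. When Visit 5 is Day 10, the later samples follow the same dose and nothing bars their use. This stands. It also means that which points enter could differ between participants in the same cohort.
- **Not every post-dose sample is idle.** A reader might infer that all Part 1 samples after the last dose go unused. Day 11 is used, so the point is confined to Day 12 and Days 13-17.
- **The individual ranges rest on an assumed CV and a chosen window.** This is fair, and the table shows the spread. Adding 5 and 6 h narrows the range but takes in more of the early phase. The washout samples are tighter at every CV tried, even with the earliest permitted third sample.
- **Reporting is by group.** At 10% CV and with residual error only, the geometric mean of six from 8, 12 and 24 h ranges over about 21-38 h. That is imprecise but not uninterpretable, so calling the Visit 5 half-life worthless would go too far.
- **Impact is small.** Clearance, accumulation and exposure-response use AUC, Cmax and Cτ, not half-life; no hypotheses are tested; and the better estimate is available only for the 12 active participants planned in Part 1. All of this stands and limits the weight of the point.

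**Conclusion.** The point holds in a limited form. Both documents assign half-life to a visit whose sampling spans about 0.8-1.1 expected half-lives, and less over the usable decline, while Part 1 samples that would estimate it better feed no named parameter. At a true half-life of 25.5 h and 10% CV, the individual 95% range is about 16-65 h from 8, 12 and 24 h, against 21-32 h or narrower from the post-last-dose samples. The ordering is the same from 5% to 15% CV. This rests on an assumed residual CV, mono-exponential decline and quantifiable late samples.

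A reader might go further and conclude that half-life should be dropped in Part 2 and replaced by effective half-life from the accumulation ratio. The documents do not support that. Effective half-life is a different quantity: the stated AUC accumulation of 2.2-2.6 gives 27-34 h, against the reported 22-29 h. Dropping half-life would also remove a stated secondary parameter from that part. The point is a cheap improvement to a secondary PK parameter and does not touch the primary antiviral endpoint.

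**What to change.** **Part 1.** In SAP 9.1.1.2, derive the terminal slope and half-life from the post-last-dose samples (Day 11, Day 12 and the Day 13-17 draw, where quantifiable), using actual times. The slope depends only on the spacing of these samples, so one rule serves whether Visit 5 was on Day 8, 9 or 10. State the points used, the minimum number and the minimum span for acceptance. Record this in SAP 2.1, which now declares no departures, as a change from protocol 10.3.2.3.

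**Part 2.** Keep half-life only where the data allow it, and flag it as resting on about one half-life or less. Optionally add effective half-life from the AUC accumulation ratio in both parts, labelled as a supportive and different quantity.

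**Cost.** SAP text and programming; no new samples or visits. There are two downsides. The half-life values of the two parts would not be directly comparable. Late 10 mg samples may also fall below the assay limit, which the documents do not give. From the predicted C24 of 56 ng/mL in protocol Table 2, the concentration at 168 h would be 56·2^(−144/22) = 0.6 to 56·2^(−144/29) = 1.8 ng/mL, against 12-18 ng/mL at 72 h.
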